6.4.5 Visit 18, 19 & 20 (12-week follow-up)

The same battery of tasks administered in visits 1 and 2 will be administered in these visits, which will occur at 12 weeks after the end of TMS. The anticipated time of these visits is 120-180 minutes. Additionally, for those subjects who had an MRI at the beginning of the study, a repeat MRI scan

The 12-week follow-up visits may be conducted via tele-assessment.

For in-person follow-up visits (i.e. not conducted via tele-assessment), the final day of the follow-up testing may include a brief tele-assessment, time permitting and with the subjects approval. This tele-assessment will consist of some combination of the tests (listed under Visits 1 and 2) conducted via video software; study personnel will conduct this tele-assessment from a nearby room.

6.6 *Subject Withdrawal*

Patients are free to withdraw from the study at any time if they no longer wish to participate. Additionally, patients may be withdrawn from the study prior to the expected completion date for a number of reasons:

- 1) Any adverse outcome or event which may represent a possible health risk to the patient
- 2) Failure of the patient to adhere to protocol requirements

3) Worsening of motor strength, language abilities, or worsening cognition or mood. Abrupt discontinuation of TMS is not associated with rebound effects or other adverse outcomes, so no alternative treatment or transitional therapy will be required if patient discontinue the protocol.

6.6.1 Data Collection and Follow-up for Withdrawn Subjects

Some patients may wish to stop receiving TMS per the protocol. In this case, attempts will be made to obtain permission to continue collecting data from motor and cognitive testing in a way that mirrors patients who are receiving TMS as specified by the protocol. Should patients wish to withdraw from the study entirely, attempts will be made to seek permission to obtain survival data on such patients throughout the protocol defined follow-up period. It will be a high priority to try to obtain at least survival data on all patients lost to follow-up. A number of attempts will be made to contact a patient by various means before he or she will be considered lost to follow-up. These methods will consist of three or more of phone calls to patient, followed by a phone call to next-of-kin if possible, followed by a certified letter. Should all of these efforts fail to elicit a response the patient will be considered lost to follow-up.

6.7 Early Termination Visits

All subjects that decide to leave the study early or are asked to by the investigator will be strongly encouraged to continue follow-up visits, but early termination visits are not planned.

7 Study Evaluations and Measurements

7.1 Medical Record Review

- Date of birth
- Address
- Contact information
- Hospital admission date and date of brain injury
- Past medical history as it relates to stroke and other neurologic conditions, cardiac status, and surgery
- Results of neuroimaging studies and dates, including MRI and/or CT exams
- Current and past medications or therapies

7.2 Physical Examination

A routine physical examination will be performed at the time of admission to the study. Should subjects report new complaints or a change in their neurologic/language status, an examination will be performed by the PI or other neurologist working on the project.

7.3 Laboratory Evaluations

All subjects who have not had high quality brain imaging in the 3 months prior to entry to the project will undergo either MRI or CAT brain imaging at the University of Pennsylvania. MR examination will include structural imaging T1- weighted magnetization prepared rapid gradient echo (MP RAGE; TR=1620 ms, TE=3.08 ms; flip= 15; FOV = 280 x 280mm, 1.0 x 1.0 x 1.0 mm voxels; 160 slices); Coplanar T2 (TR=4010 ms, TE=76ms, flip=150, FOV=256 x 256 mm, slice thickness = 2.6 mm, 48 slices); T2 –weighted resting BOLD sequence (TR = 0.5s, TE = 30ms, 230x230 mm² FoV, 128x128 acquisition matrix) and a fast fluid attenuated inversion recover scan

or FLAIR (TR=9190 ms; TE=102 ms ; flip =180; FOV= 180 x 240; 1.3 x 0.8 x 4.0 mm; 40 slice) . We will also obtain diffusion imaging (HARDI; 2.5 x 2.5 x 2.5 mm voxels, 54 slices, 60 direction b-value=2500ms/mm²); and pseudo-continuous arterial spin labeling (pCASL; TR=4000 ms; TE=18 ms; 3.4 x 3.4 x 5 mm; flip angle 90; 16 slices, matrix=64 x 64). To avoid phase wrap artifact in subjects with large heads the slice thickness may be adjusted upwards slightly.

For subject unable or unwilling to undergo MRI imaging a high-resolution CAT (60 axial slices, 3mm thick, matrix =512 x 512) without contrast will be acquired.

7.4 Pregnancy Testing

There is no known risk to a mother or fetus from TMS or MRI, but due to the fact that the safety of the technique in pregnant women has not been fully studied, pregnant women are excluded from the study. If the female subject is of child-bearing age, a urine pregnancy test will be performed before the first TMS sessions.

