1.3 Dose Rationale (if applicable)

We propose to administer 1200 pulses of TMS at 90% motor threshold on 10 occasions (Monday-Friday on consecutive weeks). This schedule was selected because it was employed in most of the studies, including our work (47), that demonstrated a beneficial effect from TMS on language function.

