3.1.3 Follow Up Phase

There will be two 3-month post-treatment visits and two 6-month post-treatment visits in which the full battery of language and cognitive assessments will be repeated. Subjects who are able to undergo MRI scanning will have anatomic and fMRI scans at or after the 6-month post-treatment visit.

All assessments listed are not mandatory. If the participant wishes to discontinue testing or refuses to perform a certain test due to frustration or fatigue, their request will be granted and not considered a deviation. Instead we will make note of any refused tests in our case report form (i.e. visit checklist).

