6.3.5 Visit 3 (Baseline 3)

Baseline testing that is not finished in the previous visit will be continued in this visit. There is the possibility that a third day will not suffice, therefore, patients may return for a 4th and 5th baseline visit.

The anticipated time of this visit is 60-180 minutes.

6.3.6 Visit 4

- MRI scan/CT scan: those subjects who are able to undergo an MRI scan will be scanned on a 3T or 1.5T Siemens unit; if subjects are unable to undergo MRI they will have a CT scan of the head. If the subject is concerned about the potential for metal fragments in the head or body, we will offer an x-ray scan to check for foreign objects in the body. No contrast will be administered.
- In cases where the baseline visits will be conducted via tele-assessment, the Ruff Figural Fluency test may be administered at this visit.

The anticipated time of this visit is 120 minutes.

If genetic sampling was not able to be collected at baseline visits, it will be collected during Visit 4.

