6.4.4 Visit 18, 19 & 20 (6-month follow-up)

The same battery of tasks administered in visits 1 and 2 will be administered in these visits which will occur at 3 months after the end of TMS. The anticipated time of these visits is 120-180 minutes. Additionally, for those subjects who had an MRI at the beginning of the study, a repeat MRI scan will be performed using the same acquisition parameters described below. The ADRS will also be collected again at the 6-month follow-up timepoint. The ADRS is completed by the participant's caregiver.

The 6-month follow-up visits may be conducted via tele-assessment.

For in-person follow-up visits (i.e. not conducted via tele-assessment), the final day of the follow-up testing may include a brief tele-assessment, time permitting and with the subjects approval. This tele-assessment will consist of some combination of the tests (listed under Visits 1 and 2) conducted via video software; study personnel will conduct this tele-assessment from a nearby room.

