8.4.2 Identifying Predictors of Treatment Response

As in our primary analyses, we will use Linear Mixed Modeling (LMM) to identify the strongest clinical/linguistic predictors of response to TMS+CILT as compared to sham TMS+CILT from among variables like chronicity, severity, gender, depression severity, naming accuracy, apraxia of speech, core semantics, and sentence processing. Although we will be underpowered for formal tests of interaction given our moderate sample size, we will refit our primary endpoint model by adding interactions of the intervention indicator and potential predictors of response to therapy to see which are suggestive of differential intervention effects. We expect that these analyses will illuminate the clinical/linguistic predictors of treatment response, thereby defining the ideal “target population” for a future Phase 3 clinical trial.

Network Neuroscience measures of response to TMS+SLT

Subjects who can undergo MRI will have studies obtained prior to treatment and at 6 months after the completion of TMS. We will construct brain networks for each individual based on their baseline and post treatment BOLD fMRI data. We will use both the AAL (132) and Glasser et al. (40) parcellations and subject-specific lesion masks to exclude lesioned areas prior to atlas registration within each subject. Then, we will extract time series data from each region following modern preprocessing practices designed to reduce the influence of motion on BOLD time series (24). Across all pairs of region time series, we will compute wavelet coherence, which is well-suited for non-stationary data such as BOLD fMRI (128), to construct an adjacency matrix A that represents the pairwise coherence across all regions within the frequency band 0.01 to 0.10 Hz,

which is robust to physiological noise and evinces reliable functional network organization (44). We will constrain our analysis to the functional connections observed among regions identified to be involved in language processing (34) and their homotopic regions. Within each subject, we will compute a within-subjects t-test for elements (connections) in A₃ (final timepoint) versus A₁ (baseline) in the language and homotopic systems corrected for multiple corrections using a false discovery rate correction with a nominal corrected p-value of 0.05. This will allow us to detect the connections most modified by treatment and determine whether mechanism 1, 2, or 3 is supported.

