12.1 Risks

12.1.1 Potential Risks

Potential risks of the behavioral and motor tasks are minimal and easily addressed (see below). The major risk associated with genetic testing is a loss of confidentiality.

There are well-known but rarely encountered risks from brain imaging with MRI and CT, or standard X-Ray exams. For the former, the risks include contrast administration (not relevant here), dislodging a metal object in the patient, interfering with an implanted device (e.g., pacemaker) and moving metallic objects in the scanner room. Protocols to deal with these issues are described below. The major risk from CT or X-rays is exposure to small amounts of ionizing radiation.

A variety of potential risks from repetitive TMS, including daily TMS administrations, have been identified (see 106 for a recent review); these include the following:

1. Seizures: Seizure induction represents the most serious known risk of TMS. The risk of seizures is quite low in subjects receiving single pulse TMS. Based on an extensive review of the literature, guidelines have been developed that specify the number of stimulations that may safely be given as a function of stimulus intensity (% of Motor Evoked Potential) and frequency of stimulation (138; see also Rossi et al, 2009). Using these guidelines there have been no published reports of seizures or evidence of after-discharge or spread of excitation in normal subjects receiving low-frequency repetitive TMS. We will adhere to the published guidelines.

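### Sections 4.2, 4.10 and 7.4 give inconsistent pregnancy-testing rules: 7.4 taken alone lets the test follow baseline imaging, and the repeat MRI is covered only on one reading of 4.10

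*Combined protocol and SAP*

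**What the plan says.** Three sections of the combined protocol and SAP set a pregnancy-testing rule.

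- **4.2 Exclusion Criteria**, among the TMS contraindications: every female participant needs a negative urine test in order to take part. The time is given only as when testing is done, with no visit named. Section 4.4 carries the 4.2 TMS contraindications into the AD sub-study.
- **4.10 Vulnerable Populations**: women of childbearing age, defined there as not postmenopausal, are asked to take a test at the start of study visits.
- **7.4 Pregnancy Testing**: for a woman of child-bearing age, "a urine pregnancy test will be performed before the first TMS sessions". The sentence before it mentions both TMS and MRI when excluding pregnancy.

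On imaging, section 6.3.6 places MRI or CT at Visit 4 and adds: "If the subject is concerned about the potential for metal fragments in the head or body, we will offer an x-ray scan". Section 7.3 limits baseline imaging to "All subjects who have not had high quality brain imaging in the 3 months prior to entry to the project". Section 12.1.1 states: "The major risk from CT or X-rays is exposure to small amounts of ionizing radiation".

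A second scan follows in the main study. Section 3.1.3 says: "Subjects who are able to undergo MRI scanning will have anatomic and fMRI scans at or after the 6-month post-treatment visit". Section 6.4.4 says that "for those subjects who had an MRI at the beginning of the study, a repeat MRI scan will be performed", and 8.4.2 says: "Subjects who can undergo MRI will have studies obtained prior to treatment and at 6 months after the completion of TMS". In the AD sub-study, 3.2.3 and 6.4.5 put the repeat MRI at 12 weeks.

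Section 12.1.2 excludes from MRI anyone who is pregnant or thinks she may be, and describes an institutional checklist and a technician interview. It names no test.

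**The concern.** A test meant to keep pregnant women out of a study should come before the first procedure for which pregnancy matters. Section 7.4 ties its only test to TMS, although imaging comes first and may involve CT or x-ray. Staff who work from 7.4 could image a woman before her pregnancy status is known and still be within the protocol.

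The differences between the three sections also have a practical side. The main study enrols from age 18 to 80 (4.1). A postmenopausal woman is ineligible without a urine test under 4.2, but needs none under 4.10 or 7.4. That invites deviations and uneven practice.

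What is at stake is participant protection and a single eligibility rule, not the trial's inference.

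**Working it through.** The plan states no figure to reproduce. The check compares texts, with a small calculation of intervals and test counts.

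**1. The three rules side by side**

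| Section | Who | When | Force |
|---|---|---|---|
| 4.2 | all female participants | when testing is done; visit not named | must be negative |
| 4.10 | women not postmenopausal | start of study visits | asked to test |
| 7.4 | females of child-bearing age | before first TMS | will be performed |

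On who is tested, 4.10 and 7.4 largely agree and 4.2 is the outlier. On timing, all three differ.

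**2. Order of procedures.** In section 6, imaging is at Visit 4 (6.3.6) and TMS at Visits 5 to 14 (6.4). The timeline in 3.1 numbers the visits differently but keeps the order: scan, then treatment. The procedure lists for screening (6.1), Visit 4 (6.3.6), treatment (6.4) and the 6-month follow-up (6.4.4) name no pregnancy test. The procedures flowchart listed as an attachment is not in the documents.

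**3. What each rule covers**

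| Rule | Baseline imaging | First TMS | Repeat MRI |
|---|---|---|---|
| 7.4 alone | not required | yes | not required |
| 4.10, start of the visit series | yes | yes | no |
| 4.10, every visit | yes | yes | yes |

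**4. Age of the 7.4 test at the repeat MRI, main study**

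- Sessions are given "on 10 occasions (Monday-Friday on consecutive weeks" (1.3), so first to last session is 11 days.
- Six months = 6 × 365.25 / 12 = 182.6 days.
- Gap from first TMS = 11 + 182.6 = 193.6 days; 193.6 / 7 = 27.7 weeks.
- With treatment counted as 14 days: 14 + 182.6 = 196.6 days; 196.6 / 7 = 28.1 weeks.
- The body of 6.4.4 says 3 months under its 6-month heading. I follow 3.1.3 and 8.4.2. At 3 months the gap would be 11 + 91.3 = 102.3 days, or 14.6 weeks.

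In the AD sub-study, 12 weeks is 84 days: 11 + 84 = 95 days, or 13.6 weeks (14 + 84 = 98 days, or 14.0 weeks). Section 8.4.3 gives 6 months for that scan instead, which would make the gap the same as in the main study.

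These are minimum gaps, since the scans are at or after the follow-up visit. On any of them, a test before first TMS says nothing about pregnancy at the repeat scan.

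**5. Tests per woman who is not postmenopausal and has the repeat MRI**

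- Under 7.4: 1.
- Under the fix, if one recent test serves first imaging and TMS: 1 + 1 = 2, so 1 extra.
- Under the fix, if the test must be repeated before TMS: 1 + 1 + 1 = 3, so 2 extra.
- A woman with no repeat MRI needs one test fewer in each case, so 0 or 1 extra.

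**The case against.** A reader might infer that the protocol as a whole allows imaging with no pregnancy test. The documents do not support that. Whether 4.10 means every visit or the start of the visit series, its test comes before the Visit 4 imaging, and 4.2 makes a negative test a condition of participation. Section 7.4 does not forbid an earlier test. The gap at baseline therefore exists only if 7.4 is the rule that governs.

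Other safeguards also count. Section 12.1.2 excludes women who are or may be pregnant, describes the MRI checklist and interview without limiting them to the first scan, and says that the CT procedure has IRB approval and its own consent form. Section 7.4 itself reports no known risk from TMS or MRI, and the radiation dose is described as small. Some subjects need no baseline imaging under 7.3. Finally, the rules can be reconciled: testing every woman at the start of every visit would satisfy all three.

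Most of this stands, and it keeps the point small. Three things remain. Section 4.10 only asks, and 4.2 names no visit, so neither settles when the test is due. The repeat MRI is covered by a test only on the every-visit reading of 4.10. Otherwise it depends on self-report and a checklist whose contents are not in the documents, in a population with moderate to severe aphasia (4.1), although a family member may complete the checklist.

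**Conclusion.** The inconsistency is real, and the safety gap is narrow. Sections 4.2, 4.10 and 7.4 differ on who is tested, when, and how firmly. Followed alone, 7.4 permits MRI, CT or x-ray before pregnancy status is known. The repeat MRI, at least 27.7 weeks after first TMS in the main study and 13.6 weeks in the AD sub-study at its 12-week time point, is covered by a test only if 4.10 means every visit.

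It would be wrong to read this as a threat to the results. The primary endpoint is change in WAB-AQ, and no pregnancy test or scan enters it. Power and type I error are unaffected. The documents do not give the number of women who are not postmenopausal, and I make no estimate. The conclusion assumes that the visit order in section 6 is followed and that the attachments, which I have not seen, do not already set one rule. This is a change worth considering because it is cheap, not one on which the trial depends.

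**What to change.** Put the same rule in 4.2, 4.10 and 7.4, for women who are not postmenopausal:

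1. A negative urine test before the first study imaging (MRI, CT or x-ray). If 7.3 means that no study imaging is needed, the test is done before the first TMS session.
2. A repeat before the first TMS session if the earlier test is not recent, within an interval that the investigators state.
3. A test before the repeat MRI: 6 months in the main study, 12 weeks in the AD sub-study. A positive result at this point cancels only the scan, and language follow-up continues.

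Add the test to the procedure lists for the visits concerned. Because screening and baseline visits may be remote (6.1, 6.3.1), say at which in-person visit the urine sample is taken.

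Cost: wording changes in three sections and the visit lists. Relative to 7.4, there are one or two extra urine tests for a woman who has the repeat MRI, and none or one for a woman who does not. Moving the existing test ahead of imaging adds no test where it is still recent at first TMS. If 4.10 was meant as every visit, the rule reduces testing, and relative to 4.2 it spares postmenopausal women. A positive test at step 3 would lose one follow-up scan from the imaging analysis in 8.4.2 (8.4.3 for the AD sub-study).

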7.5 Other Evaluations, Measures

The following battery of language and cognitive tasks will be administered prior to TMS and at 3 and 6 months after the completion of TMS: (1) The *Western Aphasia Battery* (WAB: 121) samples a number of different language functions and generates a summary score between 0-100 (Aphasia Quotient, AQ), interpretable as general aphasia severity. The WAB will be administered on two occasions prior to treatment to obtain a stable baseline. (2) The *Philadelphia Naming Test* (PNT) is a 175-item test of common object (picture) naming designed to measure retrieval of known words. Computational models have been developed that relate an individual's performance on the PNT (accuracy and error breakdown) to the integrity of semantic and phonological stages of naming (38, 136), thus producing a psycholinguistic diagnosis of the word production impairment. (3) Word and non-word repetition tests from the *Moss Psycholinguistic Aphasia Database* (MAPPD; 77) will be used to further assess lexical and post-lexical phonological encoding (31, 89). Word repetition will also be used to quantify instances of consonant distortion, prosodic alteration, and other features of speech apraxia (e.g., 105, 115). (4) The Pyramids and Palm Trees test (Picture version; 52) will be used to assess core semantic memory. (5) The *Communication Confidence Rating Scale for Aphasia* (144) will be administered to assess changes in quality of communication in daily life. (6) Narrative discourse as an indicator of functional communication will be assessed with the *Cinderella* story (145, 146). (7) Finally, 2 pre-treatment baselines will be obtained on the stimuli used for CILT. We note that the baseline sessions (T1 and T2, Figure 2) may require more than one day to complete; the entire series of baseline sessions (T1, T2 and T3) will be completed in 2 weeks or less.

One might speculate that improvements in language associated with TMS to the right IFG would be associated with adverse effects in other domains. We found no evidence of this in our previous work, nor are we aware of reports of such a phenomenon. To address this possibility, we will administer the Ruff Figural Fluency Test (108), which has been shown to be sensitive to dysfunction of the right prefrontal cortex.

While there has been research on the effects of TMS on motor recovery for patients with stroke-induced hemiparesis, we do not expect our stimulation location to have an effect on

motor ability. However, given the possibility for changes in motor ability in the hemiparetic arm, we will take a measure of grip strength using a dynamometer, and a measure of figure flexibility using the finger-tapping test. We will administer these measures at baseline, on the first, 5th and 10th day of treatment, and at the 3-month and 6-month follow up.

